6.5 Assessments of primary endpoint/outcome

Breath analysis

Prior to the measurement, participants will need to have abstained for at least one hour from smoking, eating (including chewing gum), beverages (except for plain water), brushing of teeth and using mouthwash. This should cause minimal discomfort, as participants are free to indulge in normal daily activities and dietary habits up to one hour before the beginning of the test session and immediately after its completion.

SESI-MS measurement:

- Children ≤4 years of age: for the breath analysis children are comfortably seated on a chair or on the lap of the parent and will be asked to breathe calmly as they usually breathe for about 15 seconds through a sterile mask into the mass spectrometer.
- Infants <1.5 years of age: measurements will be performed while the child is in natural sleep. The child will be in supine position either on the lap of the mother or in the cot. The face mask will be

carefully placed over the nose and mouth of the sleeping child. This procedure is entirely risk-free as no alteration of normal breathing is required. After 6 breath cycles of 15 seconds over a period of several minutes, measurement is complete.

Children ≥4 years of age: measurements will be performed via a mouthpiece. Comfortably seated participants will be asked to exhale calmly for about 15 seconds through a sterile plastic mouth piece into the MS. This procedure is entirely risk-free as no alteration of normal breathing is required – it is less demanding than routine spirometric testing. After six repeated exhalations over a period of several minutes, testing is complete.

The whole procedure will take 40 minutes.

6.6 Assessment of secondary endpoint/outcome(s)

Individual clinical history for children with respiratory symptoms and questionnaires for healthy controls:

- Children with respiratory symptoms will be characterized by their individual clinical history, including frequency and severity of exacerbations. Demographics, lifestyle and anthropomorphic characteristics will be extracted from clinical records and used in coded form for analyses. Recorded data include age, sex, ethnicity, height, weight, smoking status, comorbidities and medications, and occupation in older children. The following questionnaires and tools will be applied to assess the inclusion/exclusion criteria and the status of the patients: Asthma control and respiratory symptoms: Asthma Predictive Index (API), Paediatric Asthma Quality of Life Questionnaire (PAQLQ), Chronic Cough Quality of Life (CC-QoL), Parent Proxy Chronic Cough Quality of Life (PC-QoL).
- For the healthy controls the LuftiBus questionnaires will be applied in order to collect data on: 1. Comorbidities, personal and family history regard, environmental exposures, socioeconomic status. 2. To assess the respiratory health status (KEK-ZH-Nr. 2014-0491). This questionnaire consists of a general section where subject characteristics, such as age, origin and family, a section on the health behaviour with questions on physical activity and active smoking, a section on respiratory health including questions on colds and allergies, sleep, cough, wheezing, including asthma treatment, and a section on family history and passive smoke exposure.

Lung function (Spirometry)

Lung function will be measured in all children ≥4 years of age. In the case of a recent lung function measurement (less than 2 weeks prior to the study date) no spirometry will be performed. This is a standard procedure routinely used in medical praxis to assess the lung function. The children are asked to take the deepest breath they can, and then exhale into the lung function mouthpiece as hard as possible, for as long as possible, preferably at least 6 seconds. During the test, soft nose clips may be used to prevent air escaping through the nose. Sterile single use filter mouthpieces are used to prevent the spread of microorganisms.

The following parameters will be recorded: forced vital capacity (FVC), forced expiratory volume in first second (FEV1), peak expiratory flow (PEF), FEV1/FVC ratio, maximum expiratory flow at 75%, 50% and at 25% FVC (MEF75, MEF50, MEF25) and MEF75–25.

Fractional exhaled Nitric oxide (FeNO):

The fraction of exhaled nitric oxide (FeNO) is a non-invasive biomarker associated with airway inflammation and can be measured across all ages in standardized fashion. For the reservoir-offline technique, children are sitting on the legs of the parent or a chair while tidally breathing NO-free air for ten breaths. A reusable inert collection bag is attached to the expiratory side of a non-rebreathing valve with a resistor in place. Five breaths during relaxed tidal breathing will be sampled, and FeNO will be analysed within 4 hours using a chemiluminescence analyser. FeNO will be assessed in healthy controls only.

Allergy testing:

Airway allergies can result in significant airway inflammation. Therefore, the allergy status is important to know. Skin-prick test (SPT) for the 7 most common aeroallergens in Switzerland (D. pteronissimus,

cat, grass mix, birch, hazelnut, ash, alder) will be performed in all healthy controls. Results from allergy testing is available for all CF patients from routine clinical laboratory testing (Jahreskontrolle).

SPT is a simple, safe and quick test, providing results within 15-20 minutes. A drop of the allergen (extract) solution is placed on the skin of child comfortably seated on a chair or on the lap of the parent. The skin is then pricked through the drop using the tip of a lancet – this can feel a little sharp but is not painful and should not bleed. In case of sensitization to an allergen it elicits a small, localised allergic response, in the form of a wheal (bump) and flare (redness) at the site of testing, which disappears within 15 minutes. In the standard procedure local antihistamine gel is applied after the test to avoid itching.

Airway bacteriology

Airway and oral bacteria are metabolically active and may add to the exhaled volatile metabolites. Therefore, airway cultures need to be assessed in all children. Throat swab: two small cotton swabs will be contemporaneously used to swab the posterior nasopharynx. One will be immediately placed into the culture medium and the other one will be frozen at -80°C for further analyses (microbiome).

Exhaled breath condensate:

EBC are collected by a simple glass cold trap which is placed into a cooling sludge (T = -78.5° C, isopropanol/dry ice) following the guidelines by the ATS/ERS task force [77]. The cold trap is fixated on a table for safety and an exhaust line is applied to the cooling sludge to avoid any possible fumes from the isopropanol. The child breathes through a disposable, sterile mouthpiece into a teflon line connected to the cold trap during 5-15 minutes. The samples are immediately stored at -80°C until up-concentration by lyophilisation and analysis with ultra- high performance liquid chromatography high resolution tandem mass spectrometry (UHPLC-HRMS/MS) at either the Kinderspital Zurich or ETH Zurich.

Venous blood samples (only for children with respiratory symptoms) will be obtained during patients' routine outpatient visits if clinically indicated. The aim is to assess specific and total IgE and certain food metabolites such as fatty acids. 500µl of blood will be used to assess the total blood count. In addition, 5ml of blood shall be stored fin the CK-Care Biobank for later analyses, such as new specific nutrients and genetic analyses. Before punctuation of the child's skin EMLA® cream will be used for local anaesthetic purpose.

With their informed consent, patients with chronic respiratory symptoms agree to the strictly coded use of their confidential clinical records held by the University Children's Hospital of Zurich in present and future research purposes. One of the investigators will be responsible for extracting relevant details from the registry followed by removal of any identifying information for further analysis. Participants will be informed that other than the investigators, only authorised staff of the responsible ethics committee are allowed access to confidential information for auditing and monitoring purposes under strict adherence to patient confidentiality.

6.7 Assessment of other study variables

We designed a CRF (Clinical report form) to assess all above mentioned confounders, effect modifiers and exposers together with primary and secondary endpoints.

6.8 Assessment of safety and reporting

(HRO Art. 20. 21) [4]

This project is categorized as a non-clinical research project, risk category B.

Participants will not be subjected to any invasive or distressing test or intervention procedures beyond routine clinical management plan. Other than sparing about one hour of their time to travel to and from the Kinderspital, blowing through a sterile mouthpiece and mask, participants will not experience any additional inconveniences. All investigators and participants are fully informed about the study design and no concealment or group allocation is necessary. All measurements will be undertaken by a small set of trained investigators in a standardised fashion. Participant confidentiality is a priority.

No adverse events are expected to arise from this study.

All measurements will be supervised by medically trained investigators. All participant contact will take place in the Kinderspital, guaranteeing easy and quick access to emergency alert systems and resuscitation equipment.

The primary outcome – breath analysis – involves a single, 20 min session that asks comfortably-seated participants to exhale calmly into a plastic mouth piece and mask connected to the mass spectrometer. Participants exhale six times interspersed with adequate rest periods without excessive force into the SESI-MS. They are not exposed to any environmental hazards like radiation or chemical vapours.

Thus, breath sampling is a non-invasive, harmless, effortless procedure that is not expected to entail any distress other than the minor inconvenience of traveling to the Kinderspital Zurich.

Only procedures with minimal risk and burden (questionnaire, breath collection, lung function, throat and nasal swaps, sputum collection and skin prick testing) are applied. Healthy controls may experience some itching after skin prick test (usually up to 15 minutes) in case of having sensitization to an allergen. As a routine procedure, local antihistamine gel will be applied on that area of skin to relief and decrease the duration of itching.

Extremely rarely allergic reactions can occur within the the skin prick test, if a previously unknown severe allergy is present. This can occur because a droplet of solution containing an allergen is used during the test. These allergic reactions are mainly described in the testing of food or insect allergies (wasps and bees). The frequency is within the scope of 1-4 examinations per 10'000 tests. We only examine inhalant allergens (such as grasses, tree pollen, house dust mites and animal hair). In these allergens, reactions are much rarer. If a relevant allergic reaction still occurs, this can be treated immediately with available medicines.

6.8.1 Definition of Serious Events (SEs)

(HRO Art. 21) [4]

A **serious event** is any unfavourable event for which a causal relationship to sampling of biological material or the collection of health related personal data cannot be ruled out, and which:

- requires hospitalisation or prolongation of an inpatients' hospitalisation,
- results in persistent or significant disability or incapacity, or
- is life-threatening or results in death,

Due to the nature of the study and related study procedures no serious events are expected.

6.8.2 Assessment and Documentation of SEs

(HRO Art. 20, 21) [4]

The assessment by the project leader with regard to the project-specific measure relation is done according to the following definitions:

Unrelated: The occurrence of the event has no temporal relationship to the project-specific measures applied and can be explained by the underlying disease or other factors.

Related: There is a plausible temporal relationship between the occurrence of the event and the project-specific, applied measures and cannot be explained by the underlying disease or other factors.

All SEs are to be documented in the participants' file and on the SE report form.

6.8.3 Reporting of SEs, Safety and Protective Measures

(HRO Art. 20) [4]

The project leader shall report any occurring SE to the responsible EC within 7 days (and to the FOPH in case of involved radioactive sources). He/she shall also submit a report which evaluates the relationship between the event reported and the methods of collecting health related personal data or sampling of biological material within that project, furthermore proposals how to proceed with the project.

The project leader shall notify the EC within 7 days of any immediate other safety and protective measures, which have to be taken during the conduct of the research project. In addition, the project leader shall explain the circumstances, which necessitated the safety and protective measures.

7. STATISTICAL METHODOLOGY

7.1 Determination of Sample Size

(STROBE 10) [6]

Traditional methods for estimating sample sizes needed to detect a minimum meaningful difference cannot be applied to our exploratory pilot design. Tentative estimations can be made based on sample size requirements for factor analysis [73]: Assuming a variable-to-factor ratio of at least seven, the minimum necessary sample size for good (92%) model agreement is 55 to 80. Calculations for proteomic profiling using MS [74] suggest a similar range of sample sizes. Based on our prior experience of exploratory breath analysis [52, 55] we aim to recruit at least 60 patients with chronic respiratory symptoms with high risk for asthma, 60 patients with chronic respiratory symptoms with low risk for asthma and 60 healthy controls for WP I. We assume that we can recruit 75% of the original population to WP III, 30 allergic asthma patients, 30 no allergic asthma patients and 30 healthy controls for WP II.

7.2 Data processing

Paper documents and informed consent forms will be stored in a lock-secured cupboard in a dedicated research office at the Division of Pulmonology, University Children's Hospital of Zurich. Only study investigators have access to these documents. Authorised staff of the responsible ethics committee can request access to these data for monitoring and auditing purposes.

Electronic data will be stored in a password-secured coded spreadsheet file. The file will be stored within the Division of Pulmonology section of the University Children's Hospital of Zurich intranet server. It can only be accessed by authorised users from registered computers at the University Hospital of Zurich.

In the current study, exploratory comparisons between patients with chronic respiratory symptoms and healthy controls' breathprints shall be undertaken through statistical data reduction techniques. As previously demonstrated, this approach can drastically limit the number of compounds-of-interest – a crucial necessity for translating breathprint analysis into day-to-day clinical care [76].

7.3 Planned analysis

(STROBE 12a-d) [6]

Demographic and clinical characteristics will be compared using independent-sample pairwise analysis methods (i.e. ANOVA, t-tests, Mann-Whitney U-tests) with Bonferroni-correction for multiple comparisons. Exhaled breath composition will be evaluated through a stepwise application of statistical data reduction approaches. Bonferroni-corrected, non-parametric one-way analyses of variance (Kruskal-Wallis tests) will be employed to select significant discriminatory mass-to-charge (*m/z*) peaks. Thereafter, principle component analysis, multivariate analysis of variance and canonical analysis will be used to extract meaningful summary statistics. Data analysis will be done with Matlab (R2016b and newer, The MathWorks Inc., Natick, MA, US) and R (Development Core Team, R Foundation for Statistical Computing, Vienna, Austria) based on data analysis tools developed at ETH Zurich. The SESI-MS data will be acquired and mass calibrated with the Analyst TF 1.7 and PeakView 2.1 software (Applied Biosystems Sciex, Toronto, ON, Canada).

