Statistical Analysis incl. Power Analysis	The SESI-MS data will be acquired and mass calibrated with the Analyst TF 1.7 and PeakView 2.1 software (Applied Biosystems Sciex, Toronto, ON, Canada).

	Demographic and clinical characteristics will be compared using independent-sample pairwise analysis methods (i.e. ANOVA, t-tests, Mann-Whitney U-tests) with Bonferroni-correction for multiple comparisons. Data analysis will be done with Matlab (R2016b and newer, The MathWorks Inc., Natick, MA, US) and R (Development Core Team, R Foundation for Statistical Computing, Vienna, Austria) based on data analysis tools developed at ETH Zurich. As the study approach is exploratory, the possibilities for sample size estimation are limited. Traditional methods for estimating sample sizes needed to detect a minimum meaningful difference cannot be applied to our exploratory pilot design. Tentative estimations are done based on sample size requirements for factor analysis assuming a variable-to-factor ratio of at least seven. We have based our sample size estimation on previous research using SESI-MS.
GCP Statement:	This study will be conducted in compliance with the protocol, the current version of the Declaration of Helsinki, the ICH-GCP or ISO EN 14155 (as far as applicable) as well as all national legal and regulatory requirements.

ABBREVIATIONS

Provide a list of abbreviations used in the project plan - to be completed

BAL BMI CF DoH EC EGEP ETHZ FEV1 FVC FOPH GC-MS	Bronchoalveolar lavage Body mass index Cystic fibrosis Declaration of Helsinki Ethics Committee Essentials of Good Epidemiological Practice Eidgenössische technische Hochschule Zürich Forced expiratory volume in first second Forced vital capacity Federal Office for Public Health Gas chromatography coupled with Mass Spectrometry
HRA HRO	Federal Act on Research involving Human Beings (Human Research Act, HRA) Ordinance on Human Research with the Exception of Clinical Trials (Human Research Ordinance, HRO)
IC ID	Informed written consent
IIT	Investigator-initiated Trial
MEF75 MEF50 MEF25	Maximum expiratory flow at 75%, 50% and at 25% FVC, resp.
PEF PBB SE SESI-MS STROBE WP	Peak expiratory flow Protracted bacterial bronchitis Serious event Secondary electrospray ionization-mass spectrometry Strengthening the reporting of observational studies in epidemiology Work packages

SCHEDULE OF ASSESSMENTS (FLOW OF RESEARCH PROJECT)

Project Periods	Screening	Visits				Visits			
Visit	1	2	3	4	5	6	7	1	2 -3

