4.3 Other study variables

(STROBE #7) [6]

Assessment of potential confounders:

- bacterial colonization of upper airways
- exposure to cigarette smoke

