5.1 Type of research and general project design (STROBE 4)

Type: observational

Single center

Design:	
WP 1 / WP III	Cross sectional case control study
WPII	Longitudinal cohort study
WP IV	longitudinal assessment of asthma worsening

Our project will consist of four work packages (WP):

WP I 'preschool'; prospective cross-sectional exploratory observational matched case control study:

WP I will consist of age and sex matched case-control study including 180 preschool children aged 6 months to 4 years. It is designed for phenotyping children with chronic respiratory symptoms by SESI-MS.

Three groups will be investigated:

Healthy controls (n=60) and two groups cases stratified by diagnostic certainty: A) patients with chronic respiratory symptoms (wheezing, cough) and low risk for asthma (n=60) and B) patients with chronic respiratory symptoms (wheezing, cough) and high risk for asthma (n=60).

Asthma risk will be assessed applying the modified asthma predictive index (mAPI) and the Leicester prediction tool [14,66].

WP II 'longitudinal'; prospective longitudinal observational cohort study: For prospective assessment of health outcomes parents of the participants of WP I will be asked to take part in longitudinal follow-up study. Participants will be followed until reaching the age where lung function testing reliably can be conducted (six years). Therefore, the duration of the follow depends on the age at study entry (two to six years). Two follow-up schemes will be offered:

- 1. This scheme consists of one follow-up visit at the age six. We aim for a participation of rate 75% (n=135) of the WP I population.
- 2. For this scheme parents will be offered yearly follow-up visits until the age of six. We aim to recruit at least 45 healthy controls, 45 patients with chronic respiratory symptoms (wheezing, cough) and low risk for asthma, and 45 patients with chronic respiratory symptoms (wheezing, cough) and high risk for asthma

WP III 'school-age'; prospective cross-sectional exploratory observational matched case control study: In this case-control study we enrol three groups with sex- and age-matched school-aged children (age 5 - 18 years): A) healthy controls (n=30), B) children with known allergic asthma (n=30) and C) children with known non-allergic asthma (n=30).

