6. PROJECT POPULATION

(STROBE 6; HRO Annex 2/1.2) [4,6]

As our study approach is exploratory, thus the possibilities for sample size estimation are limited.

WP I 'preschool': 180 preschool children aged 6 months to 4 years will be included in WP 1.

Three groups will be investigated:

- 60 Healthy controls
- 60 Patients with chronic respiratory symptoms (wheezing, cough) and low risk for asthma
- 60Patients with chronic respiratory symptoms (wheezing, cough) and high risk for asthma

WP II 'longitudinal'; prospective longitudinal observational cohort study: For prospective assessment of health outcomes parents of the participants of WP I will be asked to take part in longitudinal follow-up study. Participants will be followed until reaching the age where lung function testing reliably can be conducted (six years). Therefore, the duration of the follow depends on the age at study entry (two to six years). Two follow-up schemes will be offered:

This scheme consists of one follow-up visit at the age six. We aim for a participation of rate 75% (n=135) of the WP I population.

- 45 healthy controls
- 45 patients with chronic respiratory symptoms (wheezing, cough) and low risk for asthma
- 45 patients with chronic respiratory symptoms (wheezing, cough) and high risk for asthma

WP III 'school-age'; prospective cross-sectional exploratory observational matched case control study:

In this case-control study we enrol three groups with sex- and age-matched school-aged children (age 5 - 18 years):

- 30 healthy controls
- 30 children with known allergic asthma
- 30 children with known non-allergic asthma

WP IV: 'school-age' assessment during asthma worsening.

Patients from WP III will be asked to return for two additional visits in the case of an asthma worsening. Visit Ex1 will be done within 1 week of start of asthma worsening and Visit Ex2 one month after asthma worsening is resolved. Patients with the need of an acute treatment with systemic corticosteroids or hospitalization will not be included in this part.

We aim to include 10-15 asthmatic patients from WP III

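### Bonferroni-corrected tests of background characteristics cannot support a statement that the non-randomised groups are comparable

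*Protocol*

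**What the plan says.** Protocol section 7.3 (Planned analysis) fixes the method: "Demographic and clinical characteristics will be compared using independent-sample pairwise analysis methods (i.e. ANOVA, t-tests, Mann-Whitney U-tests) with Bonferroni-correction for multiple comparisons". The synopsis, under the statistical analysis entry, repeats it. Neither place gives a significance level, the number of comparisons in the family, or the purpose of the tests.

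Section 5.1 describes WP I and WP III as case-control studies matched on age and sex. Section 4.3 has an entry headed "Assessment of potential confounders", which lists bacterial colonisation of the upper airways and cigarette smoke exposure. Section 6.7 says these are captured on the case report form.

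For the breath data, section 7.3 selects peaks with Bonferroni-corrected one-way Kruskal-Wallis tests, then applies principal component, multivariate and canonical analyses. It states no covariate.

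Section 4.2.2 lists several clinical variables as secondary endpoints: lung function, exhaled NO, allergy tests, anthropometrics, and questionnaires that include environmental exposures. Some comparisons of clinical characteristics may therefore be outcome comparisons.

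**The concern.** Patients come from a specialist outpatient clinic. Controls are classmates, siblings, or children from schools, day care and the public (section 5.3). Differences in smoke exposure, airway bacteria, treatment or household circumstances are plausible, and section 5.2 itself says that airway and oral bacteria may contribute to exhaled metabolites.

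Comparing such variables between groups serves to show how far residual confounding may reach. A confounder biases the breath comparison through the size of its imbalance and its link to the peaks, whatever its p-value. Bonferroni controls the opposite error. It also raises the bar as more characteristics are measured, so a more thorough description of the groups makes each imbalance harder to declare.

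If a corrected non-significant result were taken as evidence of balance, a peak difference driven by smoke exposure or colonisation could be credited to disease.

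**Working it through.** **The plan's own figures.** The group counts agree: 3 × 60 = 180 for WP I; 0.75 × 180 = 135 for WP II, or 45 per group; 180 + 90 = 270 in total. The range of 55 to 80 in section 7.1 comes from a cited factor-analysis rule. It cannot be rebuilt from the protocol and is not in dispute here. No power figure for characteristics is given, so there is none to reproduce.

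**Inputs from the protocol.**
- WP I: 60 per group (section 7.1: "60 patients with chronic respiratory symptoms with low risk for asthma and 60 healthy controls for WP I").
- WP III: 30 per group (section 6: "30 children with known non-allergic asthma" and two further groups of 30).

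**Assumptions, because the protocol does not state them.**
- Two-sided alpha 0.05 before correction.
- Family size m = 3 (the three pairwise group contrasts only), m = 30 (10 characteristics × 3 contrasts) or m = 60 (20 × 3).
- A true imbalance of 0.5 SD.

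**Formulas.** For a two-sample t-test with n per group:
- corrected level: α_m = 0.05/m, giving 0.0167, 0.00167 and 0.00083 for m = 3, 30 and 60;
- noncentrality: λ = 0.5 × √(n/2), which is 0.5 × √30 = 2.74 at n = 60 and 0.5 × √15 = 1.94 at n = 30;
- chance of flagging: P(|T| > t_crit), where T is noncentral t with 2n − 2 degrees of freedom and noncentrality λ;
- smallest observed difference that can be declared: t_crit × √(2/n).

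| | m = 1 (uncorrected) | m = 3 | m = 30 | m = 60 |
|---|---|---|---|---|
| WP I, chance of flagging 0.5 SD | 78% | 62% | 32% | 25% |
| WP I, smallest declarable difference (SD) | 0.36 | 0.44 | 0.59 | 0.63 |
| WP III, chance of flagging 0.5 SD | 48% | 31% | 10% | 7% |
| WP III, smallest declarable difference (SD) | 0.52 | 0.64 | 0.85 | 0.91 |

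Example for WP I at m = 60: t_crit = 3.43 on 118 degrees of freedom, so the smallest declarable difference is 3.43 × √(2/60) = 0.63 SD.

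**A binary confounder.** Take smoke exposure of 20% v 40% (assumed), with a pooled two-proportion z-test and exact enumeration. In WP I the chance of flagging is 68% uncorrected, then 50%, 22% and 17% at m = 3, 30 and 60. In WP III it is 39%, then 24%, 7% and 4%.

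**What the correction does not explain.** With no correction at all, a 0.5 SD imbalance is still missed 100 − 78 = 22% of the time in WP I and 100 − 48 = 52% in WP III. Removing Bonferroni alone would not make non-significance evidence of balance.

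**The case against.** The strongest reply is that the protocol says only that characteristics will be compared. A reader might infer that comparability will be judged by these tests, or that a p-value will decide on adjustment. No sentence says either, so that reading is not supported.

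A reader might also infer that confounding will go unadjusted altogether. The documents do not establish this: a statistical analysis plan may exist and set out adjustment. The same holds for the tests to be used for categorical variables, which the protocol does not list. That is detail a protocol commonly leaves to the analysis plan.

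The size depends on the family. The wording may mean only a correction over three pairwise contrasts, in which case the loss is 16 or 17 percentage points for a 0.5 SD imbalance (78 to 62, 48 to 31), not the steep fall seen at m = 60.

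The design also offers protection: matching on age and sex, classmate or sibling controls, one hour without passive smoking or food before measurement, and airway cultures. Where a clinical variable is a secondary endpoint, a multiplicity correction is conventional. Finally, the study calls itself exploratory (section 7.1: "Traditional methods for estimating sample sizes needed to detect a minimum meaningful difference cannot be applied to our exploratory pilot design").

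These points narrow the concern without removing it. Age and sex are covered by design, but smoke exposure and colonisation are not matched. Even at m = 3 the correction works in the wrong direction for a potential confounder. The rule is written in the protocol itself, so the concern does not depend on what an analysis plan may add.

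**Conclusion.** The point holds in a limited form. For background characteristics and potential confounders, the stated Bonferroni-corrected tests make imbalance harder to see, and their non-significance cannot carry a claim of comparability. It matters because the stated peak-selection test has no place for covariates.

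For a 0.5 SD imbalance the loss of sensitivity runs from 16 to 53 percentage points in WP I and from 17 to 41 in WP III, over 3 to 60 comparisons. All of this rests on the assumed alpha, family size and imbalance. The correction adds to a limit that small groups already impose on any significance test of balance. This is a choice that should be improved; it does not show that the groups will be wrongly declared comparable.

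**What to change.** In section 7.3 and the synopsis:

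- For background characteristics and potential confounders that neither define the groups nor measure the disease, drop the Bonferroni correction and the significance verdict. Report standardised differences (risk differences for categorical variables) with 95% confidence intervals.
- Add a sensitivity analysis that repeats the main breath comparison adjusted for the confounders named in section 4.3, whatever their p-values. These are cigarette smoke exposure and, where it is not itself part of the disease under study, upper-airway colonisation. Both are already collected.
- Keep the correction where a clinical variable is analysed as a secondary endpoint.

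Do not replace the tests with a rule that adjusts for any characteristic whose observed standardised difference exceeds a cut-off such as 0.2. Features that define the groups, such as sensitisation in WP III, would trigger it, and adjusting for them would remove the signal under study. With no true imbalance, chance alone exceeds 0.2 in about 28% of pairwise comparisons at 60 per group (t = 0.2 × √30 = 1.10) and 44% at 30 per group (t = 0.2 × √15 = 0.77).

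The cost is a short text change in two places and one additional adjusted analysis by a method that accepts covariates. No new data are needed. More imbalances will be displayed and will need comment.
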